### **Key Secondary Efficacy Analyses**

The key secondary efficacy endpoints for the current trial include:

- Average TCS during the entire RS;
- Average rhinoconjunctivitis DSS during the peak RS;
- Average rhinoconjunctivitis DMS during the peak RS.

These endpoints will be analyzed based on the FAS population using the same ANOVA model as the primary efficacy endpoint. A fixed sequence procedure will be applied to control multiplicity, where the primary efficacy endpoint will be tested first, and then the key secondary efficacy endpoints will be tested in the order stated above.

In a situation when there are more than 30% of the daily rhinoconjunctivitis DMS equal to zero, the zero-inflated lognormal model will be used as the primary analysis method for rhinoconjunctivitis DMS as appropriate; this model takes the average rhinoconjunctivitis DMS during the peak RS as response and adjusts for the same terms as in the ANOVA model.

[Table 1] summarizes the key analysis strategy for the primary and key secondary efficacy endpoints.

Table 1 Analysis Strategy for Key Efficacy Endpoints

Endpoint	Statistical Method a	Analysis Population	Missing Data Approach
Primary Efficacy Endpoint			
Average TCS during the peak RS	ANOVA	FAS	Observed data only
			LOCF
		Multiple Imputation b	
	PP	Observed data only	
	Wilcoxon Rank Sum Test;	FAS	Observed data only
Hodges-Lehmann estimate of treatment difference c			
Longitudinal Data Analysis	FAS	Model based	
Key Secondary Efficacy Endpoints			
Average TCS during the entire RS	ANOVA	FAS	Observed data only
Average rhinoconjunctivitis DSS during the peak RS	ANOVA	FAS	
Average rhinoconjunctivitis DMS during the peak RS	ANOVA Zero-inflated log-normal c	FAS	
TCS = Total Combined Score; DSS = Daily Symptom Score; DMS = Daily Medication Score; RS = Ragweed Season. ANOVA = Analysis of Variance; LOCF = Last non-missing observation carried forward. FAS = Full Analysis set; PP = Per Protocol. a Details of the statistical models are described in Section 3.2.5. b Missing data from both treatment groups will be imputed using the sample distribution of TCS observed from the placebo group. c This method will be applied if excessive zeros are observed in the data.			

### 3.1.2 Safety Analyses

An All-Subjects-as-Treated (ASaT) population will be used for safety analyses. The ASaT population includes all subjects who receive at least one dose of study treatment. Subjects will be included in the treatment group corresponding to the study treatment they actually receive during the trial.

The analysis of safety endpoints will follow a tiered approach. For this study, Tier 1 safety endpoints include:

- Proportion of subjects reporting pre-specified local application site reactions (including adverse events related to lip swelling/edema, mouth swelling/edema, palatal swelling/edema, swollen tongue/edema, oropharyngeal swelling/edema, pharyngeal edema/throat tightness, oral pruritus, throat irritation, tongue pruritus, and ear pruritus);

- Proportion of subjects reporting anaphylaxis and/or systemic allergic reactions ;
- Proportion of subjects treated with epinephrine.

Tier 1 safety endpoints will be subject to inferential testing for statistical significance with p-values and 95% confidence intervals provided for between-group comparisons. They will be analyzed using the stratified Miettinen and Nurminen method [1985] with baseline asthma status and age group as stratification factors.

### 3.1.3 Power and Sample Size

A total of approximately 1000 subjects will be randomized in a 1:1 ratio to either MK - 3641 or placebo. Assuming a 15% dropout rate, this gives approximately 425 evaluable subjects per treatment group.

With 425 subjects per arm, the study will have:

- approximately 90% power (2-sided,  $\alpha = 0.05$ ) to have the upper bound of the 95% CI for relative difference below -10%, and
- more than 90% power (2-sided,  $\alpha = 0.05$ ) to have an estimated relative difference below -15%.

See Section 3.2.7 for further details of sample size calculation.

### 3.1.4 Interim Analyses

No efficacy interim analysis is planned for this trial. Safety data will be reviewed by an external Data Monitoring Committee (eDMC) (see Section 7.3.3 of the protocol).

## 3.2 STATISTICAL ANALYSIS PLAN

This section outlines the statistical analysis strategy and procedures for the study. If, after the study has begun, but prior to any unblinding, changes are made to primary and/or key secondary hypotheses, or the statistical methods related to those hypotheses, then the protocol will be amended (consistent with ICH Guideline E-9). Changes to exploratory or other non- confirmatory analyses made after the protocol has been finalized, but prior to final database lock, will be documented in a supplemental SAP (sSAP) and referenced in the Clinical Study Report (CSR) for the study. Post hoc exploratory analyses will be clearly identified in the CSR.

### 3.2.1 Responsibility for Analyses/In-House Blinding

The statistical analysis of the data obtained from this study will be the responsibility of the designee of the sponsor.

This study will be conducted as a double-blind study under in-house blinding procedures. The official, final database will not be unblinded until medical/scientific review has been

performed, protocol violators have been identified, and data have been declared final and complete.

The randomized allocation schedule will be generated by the sponsor and implemented by the vendor of the study interactive voice response system (IVRS).

Safety will be monitored by the external Data Monitoring Committee (eDMC) on an ongoing basis and the eDMC will make recommendations to the sponsor as appropriate.

### **3.2.2 Hypotheses**

Objectives and hypotheses of the study are stated in Section 3 of the protocol.

### **3.2.3 Analyses Endpoints**

Efficacy and safety endpoints that will be evaluated for within- and between-treatment differences are listed below, followed by the descriptions of the derivations of selected endpoints.

#### **3.2.3.1 Efficacy Endpoints**

- Average TCS during the peak RS.

#### **Key Secondary Efficacy Endpoints**

- Average TCS during the entire RS;
- Average rhinoconjunctivitis DSS during the peak RS;
- Average rhinoconjunctivitis DMS during the peak RS.

#### **Tertiary Efficacy/Immunologic Endpoints**

- Average rhinoconjunctivitis DSS during the entire RS
- Change from baseline in IgE level against *Ambrosia artemisiifolia* at Visit 6 and at Visit 8;
- Change from baseline in IgG4 level against *Ambrosia artemisiifolia* at Visit 6 and at Visit 8.

#### **Exploratory Efficacy Endpoints**

- Average Asthma DSS during the peak RS, the entire RS, and the whole treatment period;
- Average daily number of puffs of as-needed SABA used during the peak RS and the entire RS;

- Average weekly number of nights with nocturnal awakening due to asthma symptoms requiring SABA use during the peak RS and the entire RS.

### **3.2.3.2 Safety Endpoints**

#### **Tier 1 Safety Endpoints**

- Proportion of subjects reporting pre-specified local application site reactions (including adverse events related to lip swelling/edema, mouth swelling/edema, palatal swelling/edema, swollen tongue/edema, oropharyngeal swelling/edema, pharyngeal edema/throat tightness, oral pruritus, throat irritation, tongue pruritus, and ear pruritus);
- Proportion of subjects reporting anaphylaxis and/or systemic allergic reactions;
- Proportion of subjects treated with epinephrine.

#### **Tier 2 Safety Endpoints**

- Proportion of subjects with any AE;
- Proportion of subjects with any serious AE;
- Proportion of subjects with any drug-related AE;
- Proportion of subjects with any serious and drug-related AE;
- Proportion of subjects who discontinue due to an AE;
- Proportion of subjects with specific AEs or SOCs (incidence  $\geq$  1% subjects in one or more of the treatment groups).

#### **Tier 3 Safety Endpoints**

- Change from baseline in laboratory test parameters at each post-baseline visit;
- Change from baseline in vital sign parameters at each post-baseline visit;
- Summaries by system organ class (SOC) for general AEs, serious AEs, drug-related AEs, and AEs resulting in discontinuation;
- Average duration of AEs in minutes on Day 1;
- Average duration of AEs in days over Day 2 to Day 14;
- Average duration of AEs in days over Day 15 to Day 28.

### 3.2.3.3 Derivations of Efficacy/Immunologic Endpoints

#### **Ragweed Season**

**Entire Ragweed Season:** the start of the entire ragweed season is the first day of 3 consecutive recorded days with a pollen count of  $\geq 10$  grains/m^3; the end of the entire ragweed season is the last day of 3 consecutive recorded days with a pollen count of  $\geq 10$  grains/m^3. This is specific for each study site.

**Peak ragweed season:** the 15 consecutive recorded days within the entire ragweed season with the highest 15-day moving average pollen count. This is specific for each study site.

#### **TCS, Rhinoconjunctivitis DSS, Rhinoconjunctivitis DMS, Asthma DSS**

These are defined in Section 4.2.3.1 of the protocol.

### 3.2.3.4 Derivations of Safety Endpoints

For laboratory tests and vital sign parameters, the baseline value is defined as the last measurement taken prior to randomization. Change from baseline in laboratory and vital signs parameters is calculated by on-treatment value minus the baseline value.

## 3.2.4 Analysis Populations

### 3.2.4.1 Efficacy Analysis Populations

The Full Analysis Set (FAS) population will serve as the primary population for the analysis of efficacy data in this study. The FAS population consists of all randomized subjects who receive at least one dose of study treatment. Subjects will be analyzed according to the treatment group to which they are randomized.

A supportive analysis using the Per-Protocol (PP) population will be performed for the primary efficacy endpoint. The PP population excludes subjects due to important deviations from the protocol that may substantially affect the results of the primary efficacy endpoints. The major protocol violations that would lead to exclusion of a subject or a data point are described below:

- Subjects with asthma requiring prescribed high daily doses of inhaled corticosteroids (as defined in the protocol);
- Subjects with chronic sinusitis during the previous 2 years;
- Subjects treated with immunotherapy within 5 years prior to screening;
- Subjects unable to meet medication washout requirements;
- Subjects randomized in the study more than once;

- Subjects who participated in the same study at another site;
- Subjects with pre-seasonal duration of treatment exposure < 56 Days;
- Subjects with a negative skin prick test response to ragweed;
- Subjects with specific IgE to ragweed < 0.7 kU/L;
- Subjects with overall treatment compliance < 75% between Visit 2 and Visit 8;
- Subjects who took prohibited medications as defined in the protocol, with the exception of antihistamines. Subjects who have taken antihistamines (other than sponsor provided rescue medications) will be considered protocol violators if they have taken the medication for 2 or more consecutive days between Visit 6 and Visit 8;
- Subjects who had their blinded treatment randomization code broken.

Analyses related to SABA use and nocturnal awakening will be based on subjects with asthma in the FAS population.

#### **3.2.4.2 Safety Analysis Populations**

The All-Subjects-as-Treated (ASaT) population will be used for the analysis of safety data in this study. The ASaT population consists of all randomized subjects who received at least one dose of study treatment. Subjects will be grouped by the study treatment actually received.

#### **3.2.5 Statistical Methods**

Statistical testing and inference for efficacy and safety analyses are described in Sections 3.2.5.1 and 3.2.5.2. Controlling of family-wise Type I error rate is described in Section 3.2.6, Multiplicity. Nominal p-values will be computed for tertiary and exploratory efficacy analyses as a measure of strength of association between the endpoint and the treatment effect rather than formal tests of hypotheses. Unless otherwise stated, all statistical tests will be conducted at  $\alpha=0.05$  (2-sided) level.

##### **3.2.5.1 Statistical Methods for Efficacy/Immunologic Analyses**

###### **Primary Efficacy Analysis**

The primary efficacy endpoint for the current trial is the average TCS during the peak ragweed season. It will be analyzed using the ANOVA model, which includes fixed effects of treatment, baseline asthma status (yes, no), age group (5 to 11 years, 12 to 17 years), pollen season, and pollen region nested within pollen season. Pollen region will be defined based on pollen station and may include several sites within an acceptable distance between the pollen counters and corresponding sites.

Two-sided 95% CI of the treatment difference in adjusted means will be presented. Also, the treatment difference in adjusted means relative to the adjusted mean of the placebo group will be presented as a percentage with corresponding 2-sided 95% CI derived using the bootstrap method. No missing data will be imputed.

The normality assumption of the ANOVA model will be checked using the Shapiro-Wilk test and inspection of the Q-Q plot. If a severe violation is observed, the primary analysis will be based on Wilcoxon Rank Sum test; the p-value will be reported together with the associated Hodges-Lehmann estimate of the treatment difference and its 2-sided 95% CI. Also, the difference in the treatment group medians relative to the median of the placebo group will be presented as a percentage with the corresponding 2-sided 95% CI derived using the bootstrap method.

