4.2 Rationale

4.2.1 Rationale for the Trial and Selected Subject Population

MK-3641 has been demonstrated to be efficacious for ragweed-allergic adults in reducing the symptoms of rhinoconjunctivitis and has an acceptable tolerability profile with few reported serious AEs (SAEs), of which none were assessed as related to the SLIT tablet. MK-3641 has yet to be studied in subjects <18 years old.

The prevalence rate of ragweed allergy in children ages 5 to 11 years and 12 to 17 years in the general population is not yet established. However, in one survey of children with asthma seen in an allergy specialty clinic, sensitization to short ragweed was 14% in young children (ages 3 to 11 years) and 25% in adolescents (ages 12 to 18 years) [6]. This study

³ RAGWITEK[®] (MK-3641) is a registered trademark of Merck & Co., Inc., Whitehouse Station, New Jersey, U.S.A.

⁴ GRASTEK[®] (MK-7243) is a registered trademark of Merck & Co., Inc., Whitehouse Station, New Jersey, U.S.A.

⁵ GRAZAX[®] is a registered trademark of ALK-Abelló A/S, Hørsholm, Denmark.

will be the first trial to evaluate the efficacy and safety of MK-3641 in children 5 to 17 years of age (inclusive).

There is no reason to first perform dose-escalation safety and tolerability studies of MK-3641 in the pediatric population when a safety and tolerable dose has been established for adults as the general dosing principal of immunotherapy treatment is the same regardless of age. This is in accordance with current allergen immunotherapy practice guidelines that recommend initiating the same dose across ages and do not recommend specific dose adjustments for children [7]. This is supported by data from similar SLIT tablet formulations (MK-7243 Timothy grass tablet and MK-8237 house dust mite tablet) that have been studied in dose-escalation and Phase 3 studies in adults and children 5 years of age and older, and the data show a similar safety profile of the same maintenance dose across age ranges [8]. The study will be stratified by age and will endeavor to enroll approximately 35% of subjects 5 to 11 years of age; this distribution is to ensure an adequate number of subjects in the younger age group are included in the study.

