5.4 Stratification

Randomization will be stratified according to the following factors:

1. Age (5 to 11 years, 12 to 17 years);
2. Asthma status (asthma, non-asthma) of the subjects.

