##### 3.1.1 Efficacy Analyses

##### Primary Efficacy Analysis

The primary analysis will be conducted on the Full Analysis Set (FAS) population. The FAS population includes all subjects who receive at least one dose of study treatment. Subjects will be analyzed according to the treatment group to which they are randomized.

The primary efficacy endpoint for the current trial is the average TCS during the peak ragweed season. It will be analyzed using the analysis of variance (ANOVA) model, which includes fixed effects of treatment, baseline asthma status (yes, no), age group (5 to 11 years, 12 to 17 years), pollen season, and pollen region nested within pollen season. Pollen region will be defined based on pollen station and may include several sites within an acceptable distance between the pollen counters and corresponding sites. To avoid failure in model convergence, observed in model testing on the blinded data, pollen region will be defined by participating countries, except for the United States, which will be split into 2 pollen regions.

Two-sided 95% confidence interval (CI) of the treatment difference in adjusted means will be presented. Also, the treatment difference in adjusted means relative to the adjusted mean of the placebo group will be presented as a percentage with corresponding 2-sided 95% CI derived using the bootstrap method. No missing data will be imputed.

The normality assumption of the ANOVA model will be checked using the Shapiro-Wilk test and inspection of the Q-Q plot. If a severe violation is observed, the primary analysis will be based on Wilcoxon Rank Sum test; the p-value will be reported together with the associated Hodges-Lehmann estimate of the treatment difference and its 2-sided 95% CI. Also, the difference in the treatment group medians relative to the median of the placebo group will be presented as a percentage with the corresponding 2-sided 95% CI derived using the bootstrap method.

A Per Protocol (PP) analysis will be conducted for the primary efficacy endpoint, where the same ANOVA model and missing data approach will be used. See Section 3.2.5.1 for further sensitivity analyses of the primary efficacy endpoint.

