### **Key Secondary Efficacy Analyses**

The key secondary efficacy endpoints for the current trial include:

- Average TCS during the entire RS;
- Average rhinoconjunctivitis DSS during the peak RS;
- Average rhinoconjunctivitis DMS during the peak RS.

These endpoints will be analyzed based on the FAS population using the same ANOVA model as the primary efficacy endpoint.

Based on the rescue medication usage from previous AIT trials, many subjects used little rescue medication during the trial, which resulted in large amounts of rhinoconjunctivitis DMS records equal to zero. Data with excessive zeroes may not conform to the normality assumption for the ANOVA model and may also prevent the proper application of non-parametric method. In a situation when there are more than 30% of the daily rhinoconjunctivitis DMS equal to zero, the zero-inflated lognormal model [16] will be used as the primary analysis method for rhinoconjunctivitis DMS as appropriate; this model takes the average rhinoconjunctivitis DMS during the peak RS as response and adjusts for the same terms as in the ANOVA model.

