### **Exploratory Efficacy Analyses**

The exploratory efficacy endpoints for the current trial include:

- Average Asthma DSS during the peak RS;
- Average Asthma DSS during the entire RS;
- Average Asthma DSS during the whole treatment period;
- Average daily number of puffs of as-needed SABA used during the peak RS;
- Average daily number of puffs of as-needed SABA used during the entire RS;
- Average weekly number of nights with nocturnal awakening due to asthma symptoms requiring SABA use during the peak RS;
- Average weekly number of nights with nocturnal awakening due to asthma symptoms requiring SABA use during the entire RS.

These endpoints will be analyzed using the same ANOVA model as the primary efficacy endpoint. Asthma DSS related endpoints will be analyzed based on the FAS population, while SABA use and nocturnal awakening related endpoints will be analyzed based on subjects with asthma in the FAS population.

In addition, components of the rhinoconjunctivitis DSS (ocular symptoms and nasal symptoms) will be summarized for the peak RS and the entire RS.

Moreover, the exploratory efficacy analyses will only consider the rescue medications provided by the study (i.e., reported in the e-diary). Some subjects may take rescue medications that are not provided by the study. A sensitivity analysis will be conducted for the following endpoints by including these rescue medications:

- Average daily number of puffs of as-needed SABA used during the peak RS;
- Average daily number of puffs of as-needed SABA used during the entire RS.

[Table 3] summarizes the key analysis strategy for the efficacy/immunologic endpoints.

Table 3 Efficacy/Immunologic Endpoints

Endpoint	Statistical Method a	Analysis Population	Missing Data
Primary Efficacy Endpoint			
Average TCS during the peak RS	ANOVA	FAS	Observed data only
			LOCF
		PP	Observed data only
	Wilcoxon Rank Sum Test; Hodges-Lehmann estimate of treatment difference c	FAS	Observed data only
	Longitudinal Data Analysis	FAS	Model based
Key Secondary Efficacy Endpoints			
Average TCS during the entire RS	ANOVA	FAS	Observed data only
Average rhinoconjunctivitis DSS during the peak RS	ANOVA	FAS	
Average rhinoconjunctivitis DMS during the peak RS	ANOVA	FAS	
	Zero-inflated log-normal c		
Tertiary Efficacy/Immunologic Analyses			
Average rhinoconjunctivitis DSS during the entire RS	ANOVA	FAS	Observed data only

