Change from baseline in IgE level against Ambrosia artemisiifolia at Visit 6 and Visit	constrained Longitudinal	FAS	Model based
Change from baseline in IgG 4 level against Ambrosia artemisiifolia at Visit 6 and Visit	constrained Longitudinal	FAS	Model based
Exploratory Efficacy Analyses			
Average Asthma DSS during the peak RS, the entire RS, and the whole treatment	ANOVA	FAS	Observed data only
Average daily number of puffs of as-needed SABA used during the peak RS and the entire RS	ANOVA	FAS (asthma only)	Observed data only
Average weekly number of nights with nocturnal awakening due to asthma symptoms requiring SABA use during the peak RS and the entire RS	ANOVA	FAS (asthma only)	Observed data only
ANOVA = Analysis of Variance; DSS = Daily Symptom Score; DMS = Daily Medication Score; FAS = Full Analysis set; IgE = immunoglobulin E; IgG 4 = immunoglobulin G 4 ; LOCF = Last non-missing observation carried forward; PP = Per Protocol; RS = Ragweed Season; SABA = short- acting beta 2 -agonist; TCS = Total Combined Score.			
a Details of the statistical models are described in Section 3.2.5.			
b Missing data from both treatment groups will be imputed using the sample distribution of TCS observed from the placebo group.			
c This method will be applied if excessive zeros are observed in the data.			

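### The analysis tables give a different trigger for the primary fallback test than the text does, and the fallback is named without the randomisation strata

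*SAP*

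**What the plan says.** **Text trigger.** Protocol 8.1.1 and 8.2.5.1 and sSAP 3.1.1 and 3.2.5.1 agree. Normality of the ANOVA is checked by Shapiro-Wilk and Q-Q plot, and "If a severe violation is observed, the primary analysis will be based on Wilcoxon Rank Sum test", reported with a Hodges-Lehmann estimate and 95% CI.

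**Table trigger.** Protocol Tables 8 and 10 and sSAP Tables 1 and 3 each have a TCS row "Wilcoxon Rank Sum Test; Hodges-Lehmann estimate of treatment difference" carrying marker c. Footnote c reads: "This method will be applied if excessive zeros are observed in the data". The same marker sits on the zero-inflated lognormal row for the medication score (DMS).

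**Zeros elsewhere.** In the key secondary analyses (protocol 8.2.5.1, sSAP 3.2.5.1) zeros concern the DMS only. If more than 30% of daily scores are zero, the zero-inflated model is used. The same paragraph warns that too many zeros may make a non-parametric method unsuitable.

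**Strata.** Protocol 5.4: "Randomization will be stratified according to the following factors", namely age group and asthma status. The ANOVA includes "fixed effects of treatment, baseline asthma status (yes, no), age group". The DMS model "adjusts for the same terms as in the ANOVA model". The Tier 1 and Tier 2 safety tests are stratified by both factors. No strata are named for the Wilcoxon fallback.

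**The concern.** A plan should hold one rule for choosing its primary test. Here the text and the tables give two, and they can disagree: a skewed TCS with no zeros meets the text rule and not the footnote. The primary test also opens the fixed sequence for all three key secondary endpoints, so ambiguity there carries down.

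The fallback could well be needed. TCS cannot fall below zero. On the planning values, zero lies 8.9/5.60 = 1.59 SD below the placebo mean and 6.78/5.60 = 1.21 SD below the active mean. A normal curve would put about 6% and 11% of subjects below zero, so some right skew is plausible, though not necessarily severe.

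If the fallback is used as named, it drops the two factors that the randomisation balances. A test that ignores factors balanced by design overstates its own variance, so it is conservative and may lose power.

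**Working it through.** **1. Triggers compared.** The text rule appears in four sections, always as severe non-normality. The footnote rule appears in four of four tables, always as excess zeros. The rules overlap, because zeros are one cause of non-normality, but they are not equivalent. In 2,000 simulated trials per setting with a gamma-shaped TCS (planning mean and SD), residuals gave Shapiro-Wilk p < 0.05 in every trial, with no zeros in the data. The p < 0.05 cut-off is assumed; the plan gives none.

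**2. The plan's power figure.** Inputs (protocol 8.2.7, sSAP 3.2.8): difference -2.12, placebo mean 8.9, SD 5.60, 425 per arm. SE = 5.60 × √(2/425) = 0.384. With the placebo mean treated as fixed, the margin beyond -10% is 2.12 - 0.89 = 1.23, and power = Φ(1.23/0.384 - 1.96) = 0.893, against the stated approximately 90%. Allowing for error in the placebo mean gives 0.920. The probability of an estimate below -15% is 0.979 to 0.986, against the stated more than 90%.

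**3. Cost of omitting the strata, by formula (normal case).** Let r be the share of TCS variance explained by the strata (assumed). With strata balanced across arms:

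- Type I error, plain Wilcoxon: 2 × [1 - Φ(1.96/√(1 - r))].
- At a true difference of -1.1, about half the planned effect, the standardised effect is z = (1.1/0.384) × √0.955 = 2.80, where 0.955 is the efficiency of the Wilcoxon relative to the t test.
- Power, plain: Φ((z - 1.96)/√(1 - r)). Power, stratified: Φ(z/√(1 - r) - 1.96).

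| r | Type I, plain | Power, plain | Power, stratified | Gain (points) |
|---|---|---|---|---|
| 0 | 5.0% | 79.9% | 79.9% | 0 |
| 5% | 4.4% | 80.5% | 81.9% | 1.4 |
| 10% | 3.9% | 81.2% | 83.9% | 2.7 |
| 20% | 2.8% | 82.6% | 87.9% | 5.3 |

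Random loss of 15% after randomisation loosens the balance. The imbalance it leaves within a stratum has 0.15 of the variance of unrestricted allocation, so 1 - r becomes 1 - 0.85r in the type I formula. That gives 4.5, 4.0 and 3.1% at r = 5, 10 and 20%.

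**4. The same by simulation.** With 1000 randomised and 15% random loss, plain Wilcoxon type I error at r = 5/10/20% was 4.1/3.8/3.0% (normal) and 4.3/3.8/2.8% (gamma).

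Power at -1.1 was simulated with 850 subjects and 4,000 runs. The age split is 35/65, from protocol 4.2.1, which "will endeavor to enroll approximately 35% of subjects 5 to 11 years of age". Assumed: 40% with asthma, permuted blocks of 4, stratum variance shared equally by the two factors. Monte Carlo error is about ±1.3 points near 80%.

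| r | Normal: plain vs stratified | Gamma: plain vs stratified |
|---|---|---|
| 0 | 79.0 vs 79.4% | 93.4 vs 93.3% |
| 5% | 80.4 vs 81.7% | 93.3 vs 94.9% |
| 10% | 81.2 vs 83.8% | 92.8 vs 96.0% |
| 20% | 82.0 vs 87.5% | 92.2 vs 97.7% |

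At -2.12 every version had at least 99.8% power.

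**5. What these shares mean.** If each factor explains r/2, the implied gap between levels is 5.60 × √((r/2)/(p(1 - p))), with p = 0.35 for age and 0.40 for asthma. At r = 20% the gaps are 3.7 and 3.6 points; at 10%, 2.6 each; at 5%, 1.9 and 1.8.

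**6. Why not also stratify by season and region.** Crossing the four strata with an assumed 5 regions × 3 seasons gives 60 cells of expected size 2.4 to 44.8. When neither strata nor region matters, power at -1.1 falls to 74.8% (normal) and 90.6% (gamma). Crossing pays only if region explains much: about 20% of variance under normal (83.0 vs 79.3%) or about 10% under gamma (93.3 vs 91.3%).

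**The case against.** **The footnote is a slip and the text governs.** Four sections give the same trigger, footnote a points to the statistical-methods section, and the warning about zeros would stop a careful reader from applying Wilcoxon on that ground. This is very likely the intent. But no precedence rule is stated, and protocol Table 10 and sSAP Table 3 lie inside the section that footnote a points to. The correction is still needed.

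**Stratifying is a preference about power.** This stands in large part. A gain of 5 to 6 points needs both half the planned effect and age and asthma gaps of about 3.7 points each, larger than the treatment effect of 2.12. The documents report no age or asthma effect on TCS. It is a free improvement, not the repair of an invalid test.

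**A stratified p-value needs a matching interval.** This stands. A van Elteren p-value beside an unstratified Hodges-Lehmann interval could disagree on significance, so both must use the same strata.

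**The word severe has no cut-off.** True. Correcting the marker leaves one trigger, but it remains a judgement.

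**Stronger readings that a reader might infer.**
- *That the fallback inflates type I error, or that the plan chose an unstratified test.* The error is conservative, and the documents never say unstratified; they leave it open.
- *That the sample size is wrong.* Its figures are reproduced above.
- *That the test could be chosen on unblinded data.* The plan does not say when normality is judged, but sSAP 3.1.1 records a region change made "To avoid failure in model convergence, observed in model testing on the blinded data", so blinded checking was already in use. Leaving treatment out of the check changes mean Shapiro-Wilk W little (0.998 vs 0.998 normal, 0.980 vs 0.972 clipped normal, 0.895 vs 0.901 gamma). No consequence is shown.
- *That the mean-based relative difference is lost under the fallback.* The text already presents it, with its bootstrap interval, without condition.

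**Conclusion.** The trigger contradiction is certain on reading alone: four tables conflict with four text sections on the primary test, and with the plan's own caution about zeros. It should be corrected whatever one thinks about the strata.

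The missing strata are a gap in specification with a small effect. The plain Wilcoxon is valid but mildly conservative: about 4% type I error if strata explain 5 to 10% of variance, about 3% at 20%. Stratifying gains about 1 to 2, 3 to 4 and 5 to 6 power points at 5, 10 and 20%, at a true difference of -1.1. It gains nothing at -2.12 and costs nothing beyond Monte Carlo error when the strata do not matter. These sizes rest on assumed variance shares, asthma prevalence, block size and distribution shape.

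**What to change.** By protocol amendment before unblinding, with the sSAP aligned:

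1. Remove marker c from the Wilcoxon/Hodges-Lehmann TCS row of protocol Tables 8 and 10 and sSAP Tables 1 and 3, or replace it there with the severe non-normality condition. Leave it on the DMS zero-inflated row.
2. Name the fallback as a van Elteren test over the four age-by-asthma strata, not crossed with season or region. Report a Hodges-Lehmann estimate and 95% CI stratified by the same four strata.

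Protocol 8.2 and sSAP 3.2 already require an amendment for a change to a primary method. The cost is wording and minor programming, with no extra subjects, visits or data. The sample size is unchanged.
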